4.2 Study Endpoints

4.2.1 Primary Study Endpoints

Version: 3.0

In order to achieve the primary objective, proving that the level of comfort of the chin and forehead rest invention attached to the existing OCT imaging devices, as opposed to the conventional existing headframes is of a higher caliber, the primary endpoint will be achieved by providing the subject with a questionnaire directly after being imaged and asking two questions: which device, C/N, provided a more comfortable experience, and on a scale of 0-5 to rate the level of comfort, as a result of the headframe, i.e. chin and forehead rest, that the subject experienced while being imaged on either device C/N.

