6.1.5 Administration

The order in which a subject will be imaged on either OCT imaging device C/N and whether the Imager will begin with either the OD/OS eye will be randomized. This will be done by providing the NYU Ophthalmology Clinic with a total of 90 envelopes that the Imager will choose from a mixed pile in which they will be evenly divided with a message to begin with device C/N and to begin with eye OD/OS.

The Standard Operating Procedure as to how to operate the novel device for imaging a subject can be seen below:

Version: 3.0

- 1. Sanitize chin and forehead rest
- 2. Seat subject by device
- 3. Move chinrest to either OD/OS
 - a. Slide chinrest to either right/left side
- 4. Size chinrest
 - a. Subject should place their chin in the rest and technician should either pull apart/push together the chin rest to either make it larger/smaller to fit the patient
- 5. Size mount of chinrest
 - a. Pull apart the mount easily to allow for the chinrest's length to be extended
- 6. Lock extension
 - a. Rotate knobs on both sides
- 7. Find correct/comfortable angular position of the chinrest
 - a. Push/move chinrest to position that it is comfortable i.e. not protruding into subject's neck and subject feels relaxed
- 8. Lock rotation
 - a. Tighten the bolt placed around the ball joint
- 9. Subject should rest forehead against the rest
- 10. Technician /imager should check if subject has to be adjusted closer to the device (based on the image from the device)
 - a. push/pull forehead rest by side of device so it will be adjusted along the grooved slot
- 11. Size forehead rest
 - a. tighten/loosen the strap on the side of the forehead rest to either make it smaller/larger for the patient (it will automatically lock into place)
- 12. Check if subject is comfortable, adjust if need be
- 13. Image subject according to scan protocol

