7.2 Imaging Procedures

- Chin and forehead rest will be adjusted for each individual subject by following the appropriate procedure, shown in standard operating procedure attached
- OCT Imaging should include for each eye
 - o Acquisition of 1 image of the Macula
 - Acquisition of 1 image of the ONH
- Two separate questionnaires will be provided to the subject before and after being imaged

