14.3 Participant Reimbursements or Payments

All participating subjects will receive \$20 as compensation for their time.

15 Interest Policy

The PI, [name], has potential conflicts of interest with this project. NYU COI committee have established a management plan that will be implemented for this project.

Version: 3.0

16 References

2. CDC. Don't Let Glaucoma Steal Your Sight! Centers for Disease Control and Prevention. Published November 24, 2020. https://www.cdc.gov/visionhealth/resources/features/glaucoma-awareness.html

3. Orbis International. Global blindness was slowing prior to pandemic study reveals. Orbis. Published October 11, 2021. https://www.orbis.org/en/news/2021/new-global-blindness-data

Version: 3.0

17 Attachments

These documents are relevant to the protocol, but they are not considered part of the protocol. They are stored and modified separately. As such, modifications to these documents do not require protocol amendments.

- 1. New Research Project Feasibility Questionnaire
- 2. Questionnaire for Subjects
- 3. Provisional Patent for the Novel Device
- 4. Recruitment telephone script

Study number: s22-01420 Version: 3.0

18 Schedule of Events

| Study team procedures X Consent subject X Select randomized imaging protocol X Clean first imaging device and attachments X Adjust chin rest / head mount X First imaging session survey X Clean second imaging device and attachments X Adjust chin rest / head mount X Image subject X Second imaging session survey X | Activity | Study Visit |
|--|---|----------------|
| ants | Study team procedures | |
| ants | Consent subject | × |
| stu | Select randomized imaging protocol | × |
| nd attachments | Clean first imaging device and attachments | × |
| nd attachments | Adjust chin rest / head mount | × |
| nd attachments | Image subject | × |
| Clean second imaging device and attachments X Adjust chin rest / head mount X Image subject X Second imaging session survey X | First imaging session survey | × |
| Adjust chin rest / head mount X Image subject X Second imaging session survey X | Clean second imaging device and attachments | × |
| Image subject X Second imaging session survey X | Adjust chin rest / head mount | × |
| Second imaging session survey | Image subject | × |
| | Second imaging session survey | × |

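### A comfort check with readjustment is written into the procedure for the novel device only, so the comfort outcome may reflect unequal checking as well as the headframe

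*Combined protocol and SAP*

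**What the plan says.** Section 6.1.5 holds the only step-by-step imaging procedure in the document, introduced with the words "The Standard Operating Procedure as to how to operate the novel device for imaging a subject can be seen below". Steps 4 to 11 size, angle and lock the chin and forehead rests. Step 12 is "Check if subject is comfortable, adjust if need be", and step 13 is imaging.

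No equivalent list exists for device C. Two other places bear on C:

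- Section 7.2, which is not limited to N: "Chin and forehead rest will be adjusted for each individual subject by following the appropriate procedure, shown in standard operating procedure attached". The only such procedure shown is the one for N, and the attachment list in section 17 names none for C.
- Section 18, which lists "Adjust chin rest / head mount" before each of the two imaging sessions.

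Neither mentions a comfort check.

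The primary endpoint in section 4.2.1 is the subject's own answer to "which device, C/N, provided a more comfortable experience", plus a 0-5 comfort rating that is to be given "as a result of the headframe, i.e. chin and forehead rest". Every subject uses both devices (section 4.1). Device order and first eye are randomised (sections 2.3 and 6.1.5). No blinding is described.

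**The concern.** Step 12 bears directly on what is scored afterwards. On N, staff must establish whether the subject is comfortable and correct any problem before the scan. On C, nothing written asks them to. The check needs no feature of the new attachment, so it could be done in the same way on a conventional rest. If it is done for one device only, part of any difference in reported comfort may come from the check and not from the headframe.

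The planned design and analysis could not detect or remove this. Randomised order balances fatigue, alertness and period effects, but a step tied to N follows N into either period. The exact test of proportion and the t test in section 10.3 both compare N with C as delivered. A larger sample does not dilute a bias of this kind; it makes a false finding more likely.

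**Working it through.** **Comparison of the text.**

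| Element before imaging | Device N | Device C |
|---|---|---|
| Written operating procedure | Section 6.1.5, steps 1-13 | None |
| Adjustment of chin and forehead rest | Sections 6.1.5, 7.2, 18 | Sections 7.2, 18 |
| Comfort check with readjustment | Section 6.1.5, step 12 | Not mentioned |

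The asymmetry that can be shown is the last row. Steps 4 to 11, including the positioning in step 7, fit an adjustable device to the subject. They belong to the intervention and are left out of the argument.

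**Inputs for the illustration.** From section 10.2: 90 subjects, null proportion 50%, two-sided exact test at 0.05, alternative 65.7%, stated power 80%. From section 5.6: enrolment of about 150. Assumed, because the documents give no figure: the preference for N that unequal checking alone would produce. Also assumed: each subject chooses N or C, and equal headframes with equal checking give 50%.

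**Rejection rule.** Find the smallest count r with P(X ≥ r | n, 0.5) ≤ 0.025.

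- n = 90: r = 55, upper tail 0.0223, attained two-sided level 2 × 0.0223 = 0.0446.
- n = 150: r = 88, upper tail 0.0204, attained two-sided level 0.0409.

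**The plan's own figure.** P(X ≥ 55 | 90, 0.657) = 0.848, so the exact test has 84.8% power against the stated 80%. The stated figure is not reproduced, but it errs on the cautious side and does not bear on this point.

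**Effect of an assumed shift.** With no true headframe effect, the chance of a significant result favouring N is P(X ≥ r | n, p):

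| Assumed preference for N from unequal checking | n = 90 (r = 55) | n = 150 (r = 88) |
|---|---|---|
| 50% (no shift) | 2.2% | 2.0% |
| 52.5% | 6.2% | 7.6% |
| 55% | 14.5% | 20.6% |

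At 55% the increase is 14.5 / 2.2 ≈ 6.6-fold with 90 subjects and 20.6 / 2.0 ≈ 10-fold with 150. The same table would describe any bias of that size. It shows how sensitive the test is, not how large this bias would be.

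**The case against.** The strongest reply is that silence is not a difference in conduct. C is the standard device, familiar to staff, and it is natural that only the new hardware has written instructions. Section 7.2 applies to both devices and section 18 schedules adjustment in both sessions. A reader might infer that subjects on C go unchecked; the documents do not show that. What stands is narrower: the check is required for N and left to the imager for C, and nothing indicates that the imager is unaware of which device is in use.

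A second reply is that individual fitting is how the invention works (sections 2.2 and 2.3), so adjustable headframe plus fitting against conventional headframe is a legitimate comparison. That is accepted for steps 4 to 11. A reader might take step 7 as further evidence of bias, but it sets the chinrest angle and is fitting. Step 12 closes the fitting sequence, so the line is a matter of judgement. It is still the one step that carries over to C unchanged, and section 4.2.1 attributes the rating to the headframe, not to headframe plus checking.

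Third, step 12 says to check. It does not say to ask, and it contains no scripted question, so the check could be made by observation. This is correct, and it means that any common wording has to be newly written.

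Fourth, some attention to comfort is device-neutral: the pre-imaging questionnaire asks every subject about discomfort, and section 18 lists a survey after each session. Neither gives a subject on C a readjustment before the scan.

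Finally, the shifts are assumed, and the 50% null needs a forced choice. Section 10.2 defines the complement of P1 as patients who report no difference; under that definition, equal headframes need not give 50%. This limits the table to an illustration.

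**Conclusion.** The point holds as a gap in the written procedure that touches the primary endpoint. Followed as written, the plan requires a comfort check with readjustment for N and none for C, and neither the randomisation nor the planned analyses can separate that from the headframe. Whether practice would differ is not known from the documents.

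The size is unknown. Under a forced choice, a 50% null and an assumed shift to 52.5% or 55%, the chance of wrongly favouring N rises from about 2% to between 6.2% and 20.6%, depending on the shift and on whether 90 or 150 subjects are analysed. A reader might conclude that the primary result would be invalid; the documents do not support that, since they neither show a difference in conduct nor give any basis for the size of a shift. The change is worth making because it is simple and the trial could not measure the effect afterwards.

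**What to change.** Add to section 6.1.5 a short parallel set-up procedure for device C: adjust the conventional chin and forehead rest within its built-in range. Then place one common comfort check immediately before imaging in both sessions, with a single wording to be written for both devices and the same chance to readjust. Show the check in both halves of the schedule in section 18.

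The cost is a paragraph of procedure and a brief added step in the C session. No endpoint, sample size or analysis changes. There are two limits. C may do slightly better than in unprompted routine use, so the estimate for N may shrink. Expectation effects from the visible attachment would remain. If the sponsor prefers to compare headframe plus its fitting and checking procedure with routine practice, section 4.2.1 should say so, and the result should not then be credited to the headframe alone.

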6.1.6 Duration of Therapy

The duration of therapy includes one imaging session in which the subject is imaged on both device A and B for both eyes and has 1 scan of their Macula and 1 scan of their ONH acquired.

For the second objective, an evaluable participant should be consistent with Section 10, Statistical Considerations and/or Statistical Analysis Plan (SAP) which will include the minimum time duration it can take for an image to be acquired which can provide a result yielding in a statistically significant value.

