| Title | Comfortable and Stabilizing Chin & Forehead Rest Attachment for Slit Lamp Configurations |
|---|---|
| Short Title | Invention Study |
| Brief Summary | Cohort will consist of 150 subjects consisting of those that are healthy or have an existing eye disease. Subjects will be imaged on two OCT devices: device N, invention attached to the device and device C, the standard conventional device. The Imager will time multiple durations, one of them which will act to evaluate the number of motion artifacts that arise due to both the instability and lack of comfort the patient is experiencing in that particular moment. Following the imaging session, subject will be asked which device was more comfortable. |
| Phase | NA |
| Objectives | The primary objective is to ascertain that the OCT Imaging device with the invention attached provides a more comfortable experience for the subject. While the secondary objective is to reduce the time it takes for the system to account for the number of motion artifacts. |
| Methodology | Randomized |
| Study Duration | Until target number of subjects is reached |
| Participant Duration | One clinic visit |
| Duration of IP administration | One clinic visit |
| Study Sites | NYU Department of Ophthalmology |
| Number of participants | 150 subjects |
| Description of Study Agent/Procedure | Comfortable chin and forehead rest that can be adjusted to fit each individual's size. |
| Statistical Analysis | Descriptive statistics for continuous variables and categorical data, presented using frequency counts and percentages will be used for group and device comparison. Patient experience will be assessed using two-sided exact test of proportion. Comfort levels of each device will be compared using t test. Linear mixed effect models will be utilized to compare the time duration while accounting for inter-eyes correlations. |

Version: 3.0

Schematic of Study Design

Screening Period

- Total n=150
- · Obtain informed consent
- Screen potential subjects by inclusion and exclusion criteria
- Obtain history, document

Day of Imaging

1. Randomize Order of Devices

 Provide clinic with 150 envelopes in which they are assigned with instructions regarding which device and eye the Imager should begin with (C/N & OS/OD)

2. Study Intervention

- Measure the length of the subject's face
- Provide subject with questionnaire containing the following
 - o Are you feeling well?
 - o Are you feeling tired today?
 - o Are you uncomfortable?

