4.2.2 Secondary Study Endpoints

A secondary objective includes evaluating various time durations while a patient is being imaged to determine whether the amount of motion artifacts are in fact being reduced by implementing the invention to existing devices. In one of the standard clinical OCT imaging devices, the Cirrus OCT, there is an eye tracking mode that can be activated whilst imaging a patient. This feature selects a specific location within the eye and will constantly adjust, i.e. track, for the fine fixation adjustments that occur when a patient's eye is moving very slightly. Therefore, in order to view whether there are a higher number of motion artifacts found in one image versus another, the Imager can time the duration it takes from the moment that they click "acquire", to when the progress bar is full. This is because the more time it takes for the system to fully acquire an image it directly correlates to how still the subject's eye is. Additionally, the data acquisition time can also be affected by whether the Imager is able to acquire a clear fundus photo, i.e. when there are no media opacities as well as if the Imager properly corrects for the refractive error.

5 Study Enrollment and Withdrawal

We aim to enroll 150 total subjects including healthy volunteers and subjects that have an existing eye disease including, but not limited to, glaucoma, AMD, DR, and CSCR. The site can actively enroll new subjects and these subjects will be are continuously followed in their institute. The total NYU cohort will include 150 healthy subjects as well as any eye related disease suspect subjects. There will be no enrollment restrictions based on gender, ethnic origin or HIV status and the study population will reflect the demographics of NYU Department of Ophthalmology. Subjects from clinical groups will participate in all applicable sub-studies of the protocol.

Subjects will be included in both groups, labelled as either Group 1 (Novel) or Group 2 (Conventional). Both groups will include subjects that are identified with glaucoma, age related macular degeneration, diabetic retinopathy, and central serous chorioretinopathy or any other eye related disease as well as healthy volunteers that are recruited from the clinic that undergo the clinical examination as part of their routine clinical management and healthy volunteers that are invited to the clinic to undergo the clinical examination for the purpose of the study.

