10.1 Statistical Hypotheses

We hypothesize there will be a significant difference between the patient's experience in terms of comfort while being scanned using the attachment of the chin and forehead rest mounted on the existing ophthalmic devices. Additionally, we expect to see a significant improvement in time duration of adjusting motion artifacts.

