10.3 Statistical Methods

Unless otherwise specified, descriptive statistics for continuous variables include the number of patients with data (N), mean, standard deviation (SD), median, minimum, and maximum. The same number of decimal places as in the observed value are presented when reporting median, minimum, and maximum; one more decimal place than in the observed value is presented when reporting mean and quartiles; and two more decimal places than in the observed value is presented when reporting SD.

Categorical data are presented using frequency counts and percentages. All percentages are rounded to one decimal place, unless otherwise specified. Percentages equal to 100 are presented as 100% and no percentages are presented for zero frequencies. Where individual variable values are missing, summaries of categorical data are based on reduced denominators (i.e., the denominators include only patients with available data) and the number of missing values is presented.

The improvement of patient's experience in terms of comfort will be assessed using two-sided exact test of proportion to compare P_1 and P_0 . Further, the comfort levels of each device from all patients will be compared using t test. Linear mixed effect models will be utilized to compare the time duration of adjusting motion artifacts between two devices while accounting for inter-eyes correlations. The p values less than 0.05 will be considered as significant.

10 Source Documents and Access to Source Data/Documents

Source data is all information, original records of clinical findings, observations, or other activities in a clinical trial necessary for the reconstruction and evaluation of the trial. Source data are contained in source documents. Examples of these original documents, and data records include: hospital records, clinical and office charts, laboratory notes, memoranda, subjects' diaries or evaluation checklists, pharmacy dispensing records, recorded data from automated instruments, copies or transcriptions certified after verification as being accurate and complete, microfiches, photographic negatives, microfilm or magnetic media, x-rays, subject files, and records kept at the pharmacy, at the laboratories, and at medico-technical departments involved in the clinical trial. It is acceptable to use CRFs as source documents. If this is the case, it should be stated in this section what data will be collected on CRFs and what data will be collected from other sources.

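### The evaluable set for the secondary time objective is tied to acquisition time and significance but never defined, and the time model names only inter-eye correlation, so its 5% level is not assured

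*Combined protocol and SAP*

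**What the plan says.** Section 6.1.6 (Duration of Therapy): "For the second objective, an evaluable participant should be consistent with Section 10" and/or the SAP, which is to include "the minimum time duration it can take for an image to be acquired which can provide a result yielding in a statistically significant value".

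Section 4.2.2 defines the quantity being timed: "the Imager can time the duration it takes from the moment that they click" to start the acquisition until the progress bar completes. Acquisition time is therefore the outcome of the second objective. Section 10.1 states the expectation: "we expect to see a significant improvement in time duration of adjusting motion artifacts".

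Section 10.3 gives the analysis: "Linear mixed effect models will be utilized to compare the time duration of adjusting motion artifacts between two devices while accounting for inter-eyes correlations". It adds: "The p values less than 0.05 will be considered as significant". The Protocol Summary repeats the same single feature: "Linear mixed effect models will be utilized to compare the time duration while accounting for inter-eyes correlations".

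On the number of scans, Section 6.1.6 says that the subject is imaged on both devices, in both eyes, and "has 1 scan of their Macula and 1 scan of their ONH acquired". Section 7.2 makes this one macula and one ONH image for each eye.

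Sections 10.1 to 10.3 contain no minimum time, evaluable participant, analysis set or random-effects list for the time objective. They do not say whether macula and ONH times are pooled.

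**The concern.** Two gaps bear on the same secondary test.

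**(a) Evaluable set.** Membership is linked to the outcome (acquisition time) and to the result (a significant value), and the definition is deferred to a section that does not hold it. Nothing says that the value is set before times are seen. Section 8.1.1 has a group that includes the PI and sub-investigators reviewing cumulative acquisition times every two months. That shows no intent, but it means that times will be visible while the rule is still open.

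**(b) Time model.** Inter-eye correlation does not cover what a participant's four scans on one device have in common. The protocol gives reasons to expect some sharing. Section 2.3 says that imaging time may depend on alertness, energy and how the subject feels. Section 18 schedules two successive sessions, each with its own adjustment. Section 6.1.5 sizes the attachment to the individual. Against that, Section 6.1.5 also moves the chinrest between eyes, so the amount shared is unknown. If the device difference does vary between participants and no term allows for it, the standard error is too small and more participants do not cure it.

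At stake is whether a p value below 0.05 for time means what it says.

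**Working it through.** **Plan's own figure.** There is none to reproduce. The documents give no effect size, SD, power or sample size for time; Section 10.2 concerns the comfort proportion only. Every variance ratio and cut-off grid below is an assumption.

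**Scan count.** 2 devices x 2 eyes x 2 scan types = 8 scans, 4 per device. That all eight are timed is an inference.

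**(a) Three readings of the clause**, simulated with no device effect (n = 90 and 150, eight settings of 5,000 runs, participant kept if the mean or shortest time exceeds a percentile cut):

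- A device-neutral floor fixed in advance: 4.3-5.8% for any single cut, i.e. about 5%.
- A minimum detectable difference: this selects nobody, so 5%.
- A cut-off chosen for the smallest p value: cuts {0, 10%} 6.7%; {0, 20%} 7.3%; {0, 10, 20%} 8.2%; {0, 20, 40%} 9.5%; six cuts from 0 to 50% 12.2%. A separate simulation with log-normal times and 3 to 11 cuts gave 9.8-11.0%, and 4.1-5.2% for a fixed cut.

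**(b) Omitted participant-by-device term.** Set residual variance to 1. Let r be the participant-by-device variance and e the eye-within-participant variance, both relative to residual.

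*Pooled, 8 scans.* The variance of a participant's mean N-minus-C difference is 2r + 2/4 = (1 + 4r)/2. A model without the term uses its residual mean square M in place of 1 + 4r. The 7 within-participant degrees of freedom have expected mean squares of 1 + 4r (device), 1 + 4e (eyes) and 1 (the other five). So:

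- participant and eye intercepts: M = (1 + 4r + 5)/6 = 1 + 4r/6
- participant intercept only: M = 1 + 4(r + e)/7

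*Scan types separate, 4 scans each.* The correct quantity is 1 + 2r. M = 1 + r with participant and eye intercepts, and 1 + 2(r + e)/3 with a participant intercept only.

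Two-sided error = 2Φ(-1.96 √(M / correct quantity)). Example, pooled with participant and eye intercepts, r = 0.25: M = 1.167, correct quantity 2, ratio 0.583, square root 0.764, 1.96 x 0.764 = 1.497, error 13.4%.

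| Analysis and fitted intercepts | r = 0 | 0.1 | 0.25 | 0.5 |
|---|---|---|---|---|
| Pooled; participant and eye | 5.0% | 8.7% | 13.4% | 19.1% |
| Pooled; participant only, e = 0 | 5.0% | 8.9% | 13.8% | 19.9% |
| Pooled; participant only, e = 0.5 | 2.6% | 5.5% | 9.8% | 15.6% |
| Separate; participant and eye | 5.0% | 6.1% | 7.4% | 9.0% |
| Separate; participant only, e = 0 | 5.0% | 6.5% | 8.4% | 11.0% |
| Separate; participant only, e = 0.5 | 2.4% | 3.4% | 5.0% | 7.4% |

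A false finding in favour of device N is half of each figure.

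*Simulation check of the first row.* n = 150, e = 0.5, 20,000 runs: 5.1%, 8.7%, 14.1%, 19.0%. An independent run at n = 90 gave 4.8%, 9.0%, 13.1%, 18.7%. A participant-level paired test stayed at 4.8-5.3% in all 32 settings of the 20,000-run check.

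**Interval width after adding the term** = 1/√ratio, at r = 0, 0.1, 0.25, 0.5. Pooled, against participant and eye intercepts: 1.00, 1.15, 1.31, 1.50. Pooled, against participant only with e = 0.5: 0.88, 1.02, 1.18, 1.38.

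**The case against.** The strongest reply is that both parts treat brevity as error. Section 6.1.6 is one garbled sentence, and two of its three readings leave the level intact. The 7-12% range needs a search that no section describes, on grids that the documents do not supply. Section 10.3 names one feature of the model without excluding others, and a participant intercept is itself a natural way to account for two correlated eyes. With that intercept, scan types separate and e = 0.5, error is at or below 5% up to r = 0.25. Only a secondary objective is involved.

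Most of this stands, and it limits the point. A reader might infer that the sponsor intends to choose participants by p value, or that the time test is inflated as planned. The documents support neither: the sentence is ambiguous, no variance is given, and the error can lie on either side of 5%.

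What does not stand is that nothing needs changing. Read literally, the clause selects on outcome and significance, and the cross-reference leads nowhere. Two fair readings of the model sentence can give materially different error rates on the same data.

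A smaller objection is also right: the paired test and the mixed model are not exactly equivalent. Mixed-model software holds variance components at or above zero; with no participant-by-device variance, simulation gave 4.4-4.7% for the model against 4.9-5.1% for the paired test.

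**Conclusion.** The point holds as a gap in specification for the secondary time objective: the 5% level is not assured, which is weaker than saying that it is breached. For (a), the level is about 5% unless a cut-off is chosen by its p value; then it is roughly 7-12% under the assumed grids. For (b), it is about 9%, 13-14% and 19-20% at assumed ratios of 0.1, 0.25 and 0.5 when scans are pooled with participant and eye intercepts, or with a participant intercept only and no eye variance. It is lower with scan types separate, or with a participant intercept only when eyes differ, and can fall to about 2.4%. If the ratio is zero or the model includes the term, (b) causes no inflation. The primary comfort endpoint is untouched. This is a cheap improvement, not a threat to the trial's main conclusion.

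**What to change.** **Section 6.1.6.** Delete the clause on minimum time and significance, and write:

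> *Evaluable for the second objective: every randomised participant with at least one timed scan, regardless of acquisition time or statistical significance.*

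**Section 10.3.** Write:

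> *Acquisition time will be analysed in a linear mixed model with device and scan type as fixed effects and random effects for participant, eye within participant and participant-by-device.*

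This pools macula and ONH times explicitly. A paired test of each participant's mean N-minus-C difference, in participants timed on both devices, is a near-equivalent check when data are complete. The handling of failed or repeated scans, on which Section 10 is also silent, should be settled in the same edit. All of this should be fixed before times are analysed.

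**Cost.** Text in two sections; no new data or visits. The price is precision. Against a participant-and-eye model without the term, the pooled interval is about 15-50% wider if the variation exists at these ratios, and essentially unchanged if it does not. Against a participant-intercept-only model with eye variance 0.5, it ranges from about 12% narrower to 38% wider.
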